5.1 Inclusion criteria

General and Demographic Criteria

- 1. Age of 18 to 50 years
- 2. Access to a participating CRS and willingness to be followed for the planned duration of the study
- 3. Ability and willingness to provide informed consent
- 4. **Assessment of understanding**: volunteer demonstrates understanding of this study and completes a questionnaire prior to first infusion with verbal demonstration of understanding of all questionnaire items answered incorrectly
- 5. Agrees not to enroll in another study of an investigational research agent for the duration of the participant's trial participation
- 6. **Good general health** as shown by medical history, physical exam, and screening laboratory tests

HIV-Related Criteria:

- 7. Willingness to receive HIV test results
- 8. Willingness to **discuss HIV infection risks** and amenable to HIV risk reduction counseling

- 9. **Persons born Male or identifying as Transgender (TG)** (male-to-female or female-tomale, see HVTN 704/HPTN 085 SSP) who, in the 6 months prior to randomization, experienced 1 or both of the following HIV risk criteria:
 - Condomless anal intercourse with 1 or more male or transgender partner(s)
 - Anal intercourse with 2 or more male or transgender partners

Note: Receipt of hormonal therapy does not make a TG volunteer ineligible.

Volunteers who have been in a mutually monogamous relationship with an HIV-1 seronegative partner for > 1 year are excluded.

Laboratory Inclusion Values

Hematology

- 10. **Hemoglobin** (Hgb) \geq 10.5 g/dL for volunteers who were born female, \geq 13.0 g/dL for volunteers who were born male (\geq 12.0 g/dL for transgender women taking feminizing hormones [eg, anti-androgens, estrogens])
- 11. Platelets \geq 100,000 cells/mm³

Chemistry

12. ALT < 2.5 times the institutional upper limit of normal and creatinine \leq 1.25 times the institutional upper limit of normal

Virology

13. HIV uninfected, as defined in the SSP, within 30 days prior to enrollment

Urine

14. Negative, trace, or 1+ (30 g/L for semi-quantitative) urine protein by dipstick

Reproductive Status

- 15. Volunteers capable of becoming pregnant: negative serum or urine beta human chorionic gonadotropin (β-HCG) pregnancy test performed at the screening visit and prior to infusion on the day of initial infusion. Persons who are NOT capable of becoming pregnant due to having undergone total hysterectomy or bilateral oophorectomy (verified by medical records) are not required to undergo pregnancy testing.
- 16. **Reproductive status**: A volunteer who is capable of becoming pregnant must agree to consistently use effective contraception (see Appendix B, and SSP) for sexual activity that could lead to pregnancy from at least 21 days prior to enrollment through the last required protocol clinic visit.
- 17. Volunteers capable of becoming pregnant must also agree not to seek pregnancy through alternative methods, such as artificial insemination or in vitro fertilization until after the last required protocol clinic visit

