6.2 Study product formulation

VRC-HIVMAB060-00-AB [VRC01, Labeled as VRC01 HIV MAb Drug Product VRC-HIVMAB060-00-AB]

VRC01 will be provided as a sterile clear, colorless to yellow isotonic solution, essentially free of visible particles; some opaque or translucent particles may be present. Each vial contains 100 mg / mL of VRC-HIVMAB060-00-AB in formulation buffer. The formulation buffer is composed of 25 mM sodium citrate, 50 mM sodium chloride, and 150 mM L-arginine hydrochloride at pH 5.8. Vials are intended for single use only and do NOT contain a preservative. The product should be stored frozen -35°C to -15°C with excursions permitted between -45°C and -10°C. The study products are described in further detail in the IB.

Prior to preparation, vials containing VRC01 must be removed from the freezer and thawed for a minimum of 1 hour at room temperature. Following this 1 hour thaw, the unopened vials of VRC01 may be stored for up to 24 hours at room temperature (not to exceed 27°C) and/or up to 4 weeks at 2°C to 8°C. Product may NOT be thawed or stored in direct sunlight. Once thawed, product may NOT be refrozen.

VRC01 is a highly concentrated protein solution and may develop white-to-translucent particles after thawing. These particles have been observed in approximately 1-3% of the vials and generally disappear over a few hours at room temperature. Particle formation has no effect on product quality. If the particles do not disappear at room temperature, the vials should be placed in the refrigerator, as particles may continue to dissipate at 2°C to 8°C (36°F to 46°F). Vials that continue to have visible particles after a maximum of 24 hours at controlled room temperature and/or after 4 weeks at 2°C to 8°C (36°F to 46°F) should not be used. Instead, those vials with particles still visible should be quarantined [at 2°C to 8°C (36°F to 46°F)] until they are returned to the NIAID Clinical Research Products Management Center (CRPMC) (or manufacturer upon request of the CRPMC) or destroyed if directed by the CRPMC.

Control for VRC01 [Sodium Chloride for Injection USP, 0.9%]

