7.9 Urine testing

Urine dipstick testing may be performed in the clinic or the lab. The following analytes should be analyzed and recorded: specific gravity, protein, blood/hemoglobin, pH, urobilinogen, bilirubin, ketone, leucocyte esterase, nitrite, and glucose. The examination is performed on urine obtained by clean catch. Urine microscopy is required when the protein result is 1+, 2+, 3+, or 4+ (or semi-quantitative 30, 100, 300, or 2000 g/L) and/or the blood/hemoglobin result is trace, 1+, 2+, 3+, or 4+, but not required (unless otherwise clinically indicated) if the dipstick result is abnormal due to non-urinary bleeding.

If the dipstick performed for screening is transiently abnormal with an exclusionary result (eg, 2+ proteinuria), then repeat the dipstick and, if within the eligibility limits specified in the protocol, the participant may be enrolled (see SSP for further detail).

A follow-up urine test should be deferred if a participant is experiencing non-urinary bleeding (eg, menstruation), but should be performed as soon as possible. If a follow-up dipstick is abnormal due to non-urinary bleeding (eg, a participant's menstrual period), document in the comment section of the CRF and repeat the dipstick once the participant is no longer experiencing non-urinary bleeding. In this case, a urine microscopy is not required (see SSP for further detail). If a follow-up dipstick is abnormal due to infection, document this issue in the participant's source documentation and provide appropriate treatment and/or referral.

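### The urine-protein scale in criterion 14 and Section 7.9 is printed in g/L, which is impossible at its top step, so the numbers cannot match the plus grades beside them

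*Protocol*

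**What the plan says.** Criterion 14 in protocol Section 5.1 sets the urine-protein entry limit twice in one line, as a plus grade and as a number: "Negative, trace, or 1+ (30 g/L for semi-quantitative) urine protein by dipstick".

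Section 7.9 repeats the scale for a different purpose. Microscopy is required when protein is anywhere from 1+ to 4+, "or semi-quantitative 30, 100, 300, or 2000 g/L". It is also required on a second, separate ground: "and/or the blood/hemoglobin result is trace, 1+, 2+, 3+, or 4"+ (findings caused by non-urinary bleeding are exempt). The same section says what to do when a screening dipstick is "transiently abnormal with an exclusionary result (eg, 2+ proteinuria"), so 2+ is treated as outside the entry limit without reference to any unit.

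Section 7.9 lets the dipstick be done in the clinic or the laboratory, and Appendix F assigns it to local laboratories. In Schedule 1 it is done at screening, Week 8 and Week 80 (Appendices F and J).

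**The concern.** A concentration of 2000 g/L cannot occur in urine or in any other aqueous sample. Because the unit is the same in both sections, the error is not confined to the top step: the 30 g/L in criterion 14 belongs to the same scale.

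The numbers are operative. Criterion 14 offers 30 g/L for results reported semi-quantitatively, and Section 7.9 joins its list to the plus grades with an or. For a site that reports numerically, the number is the rule. If number and grade disagree about the same specimen, one entry criterion has two meanings, and so does the trigger for a safety work-up. Laboratory measures of safety are part of primary endpoint 1 (Section 3.1), so both should mean the same thing at every site.

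**Working it through.** No sample-size or error-rate formula applies. The check is a unit conversion and a mass-per-volume comparison.

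**Inputs**
- Steps for 1+, 2+, 3+ and 4+: 30, 100, 300 and 2000, printed as g/L (Section 7.9). The 30 g/L step is repeated in criterion 14.
- Benchmark from the protocol itself: "Each vial contains 100 mg / mL of VRC-HIVMAB060-00-AB in formulation buffer" (Section 6.2). The same section says "VRC01 is a highly concentrated protein solution and may develop white-to-translucent particles after thawing".
- Exclusionary example by grade: 2+ (Section 7.9).

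**Step 1. Read the scale as printed.** Dividing by 1000 gives kg of protein per litre: 0.03, 0.1, 0.3 and 2.0. The last is about twice the mass of a litre of water. Even if a litre of pure solid protein weighed 1.0 to 1.5 kg (an assumption), 2 kg would exceed it by a factor of 2/1.5 = 1.33 to 2/1.0 = 2. The printed scale cannot be reproduced as a real measurement scale.

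**Step 2. Compare with the drug vial.** 100 mg/mL × 1000 mL/L ÷ 1000 mg/g = 100 g/L. Relative to that concentrated antibody solution, the printed steps are 30/100 = 0.3, 100/100 = 1, 300/100 = 3 and 2000/100 = 20 times as strong. Urine graded 2+ would carry as much protein as the product vial.

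**Step 3. Convert under the candidate units.** The documents name neither alternative, so both are assumptions. The conversions are mg/dL × 0.01 = g/L and mg/L × 0.001 = g/L.

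| Grade | Printed (g/L) | If mg/dL, in g/L | If mg/L, in g/L |
|---|---|---|---|
| 1+ | 30 | 0.3 | 0.03 |
| 2+ | 100 | 1 | 0.1 |
| 3+ | 300 | 3 | 0.3 |
| 4+ | 2000 | 20 | 2 |

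Size of the error: 30/0.3 = 100-fold if mg/dL, and 30/0.03 = 1000-fold if mg/L.

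**Step 4. Set the converted steps against the printed 30 g/L.** The highest step, 4+, is 20 or 2 g/L, and both are below 30. So under either unit no step from 1+ to 4+ reaches the printed figure.

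**Step 5. One specimen, two answers.** Take a true result of 1 g/L. If the steps are mg/dL, it is exactly 2+. If they are mg/L, it falls between 3+ (0.3) and 4+ (2). By grade it is outside the entry limit and calls for microscopy. By number, if 30 g/L is taken as a ceiling, it is admitted and does not meet the protein trigger.

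**The case against.** The strongest case on the other side is that this is a mislabelled unit with little practical reach. Most of that case stands.

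- **The plus grades work alone.** Criterion 14 names the admissible grades, and Section 7.9 names the grades that need microscopy and calls 2+ exclusionary. A site reading grades applies both rules correctly whatever unit is printed. This stands.
- **The numbers are step labels, not written ceilings.** Neither section states an inequality. A result of 1 or 3 g/L matches none of the listed values, so a site may notice the mismatch and go back to the grade. This stands, and it is why the consequence is conditional.
- **Other rules overlap.** Blood or hemoglobin at trace or above triggers microscopy independently. The creatinine limit, the exclusion of known renal dysfunction and exclusion 9 (clinically significant abnormal laboratory results) can each catch some affected volunteers. None of them is a protein limit, so the protection is partial.
- **No exposed site is shown.** The documents do not identify a site that reports only in g/L, and the study-specific procedures to which Section 7.9 refers are not available here.
- **Inference is barely touched.** The laboratory boxplots named in SAP Appendix A do not include urine protein. Eligibility is settled before randomization, which is blocked and double-blind, so uneven reading by site would not favour an arm.

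A reader might go further and infer that g/L sites would admit heavy proteinuria and that microscopy would never be triggered. The documents do not support that. It requires a site with numeric g/L results, no plus grade, and a literal use of 30 as a ceiling, and even then the blood trigger remains.

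What the objection does not remove is the error. The safeguards work when the site ignores the printed number or when something else is abnormal. A text-extraction fault is unlikely, since the same unit appears in two separate sections and other units are intact.

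**Conclusion.** The point holds in a limited form. The printed g/L scale is wrong in both sections, and this is certain from the 2000 g/L step alone. The numbers therefore cannot be equivalents of the plus grades beside them.

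The size of the error depends on an unstated unit: 100-fold if mg/dL, 1000-fold if mg/L. It is tempting to quote 100-fold as fact, but the documents give no dipstick scale and that figure is only one end of the range. The conclusion that every step through 4+ lies below 30 g/L holds at both ends.

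The consequence is possible but not shown. A site working from a numeric g/L result without a plus grade could admit a volunteer at 2+ or above, or omit microscopy that the protein grade calls for. Power, type I error, event counts and the efficacy analysis are unaffected. The SAP (Section 1) has enrollment ending by September 30, 2018 at the latest, so after that date the entry side is a matter of checking past screening results.

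**What to change.** Three steps, none of which changes an eligibility or work-up rule:

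1. The sponsor confirms the intended unit against the scale of the dipsticks in use.
2. Criterion 14 and Section 7.9 are corrected together, so that the numeric equivalents agree with the plus grades already stated. The plus grades stay as they are, and no new threshold is introduced.
3. Any site that used numeric g/L results is asked to check its screening and on-study urine-protein results against the plus grade and to report discrepancies.

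The cost is two unit corrections and a short site memo, plus a limited record check at any site that reported in g/L.

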5.2 Exclusion criteria

General

- 1. Investigational research agents received within 30 days before first infusion
- 2. Body mass index (BMI) ≥ 40
- 3. Pregnant or breastfeeding
- 4. Any reactive, indeterminate, or positive HIV test, even if subsequent testing indicates that the individual is not HIV infected, except as permitted by the HVTN 704/HPTN 085 PSRT.

Vaccines

5. **HIV vaccine(s)** received in a prior HIV vaccine trial. For volunteers who have received control/placebo in an HIV vaccine trial, the HVTN 704/HPTN 085 PSRT will determine eligibility on a case-by-case basis.

Immune System

- 6. Serious adverse reactions to VRC01 formulation components such as sodium citrate, sodium chloride, and L-arginine hydrochloride, including history of anaphylaxis and related symptoms such as hives, respiratory difficulty, angioedema, and/or abdominal pain.
- 7. **Autoimmune disease**, including Type I diabetes mellitus (Not excluded from participation: Volunteer with mild, stable and uncomplicated autoimmune disease that does not require consistent immunosuppressive medication and that, in the judgment of the site investigator, is likely not subject to exacerbation and likely not to complicate reactogenicity and AE assessments)

8. Immunodeficiency syndrome

Clinically significant medical conditions

- 9. Clinically significant medical condition, physical examination findings, clinically significant abnormal laboratory results, or past medical history with clinically significant implications for current health. A clinically significant condition or process includes but is not limited to:
 - Any contraindication to repeated infusions or blood draws, including inability to establish venous access;
 - A condition that requires active medical intervention or monitoring to avert grave danger to the volunteer's health or well-being during the study period; or
 - A condition or process for which signs or symptoms could be confused with reactions to VRC01.
- 10. Any medical, psychiatric, occupational, or other condition that, in the judgment of the investigator, would interfere with, or serve as a contraindication to, protocol adherence,

assessment of safety or infusion reactions, or a volunteer's ability to give informed consent

- 11. **Psychiatric condition that precludes compliance with the protocol**. Specifically excluded are persons with psychoses within the past 3 years, ongoing risk for suicide, or history of suicide attempt or gesture within the past 3 years.
- 12. Asthma, other than mild, well-controlled asthma
- 13. **Bleeding disorder** diagnosed by a doctor (eg, factor deficiency, coagulopathy, or platelet disorder requiring special precautions)
- 14. **Malignancy** (Not excluded from participation: Volunteer who has had malignancy excised surgically and who, in the investigator's estimation, has a reasonable assurance of sustained cure, or who is unlikely to experience recurrence of malignancy during the period of the study)
- 15. Seizure disorder: History of seizure(s) within past three years. Also exclude if volunteer has used medications in order to prevent or treat seizure(s) at any time within the past 3 years.
- 16. History of hereditary angioedema, acquired angioedema, or idiopathic angioedema
- 17. History of **receiving transplantation of life-saving organs or tissues** (includes heart, kidney, pancreas, lungs, liver, and intestines)
- 18. Known hepatic or renal dysfunction

5.3 Participant departure from infusion schedule or withdrawal

This section concerns an individual participant's departure from the infusion schedule. Pause rules for the trial as a whole are described in Section 10.3.

5.3.1 Delaying infusions for a participant

Under certain circumstances, a participant's scheduled infusion will be delayed. The factors to be considered in such a decision include but are not limited to the following:

- Prior to infusion, abnormal vital signs or clinical symptoms that may mask assessment of a study product reaction
- Intercurrent illness that is assessed by the site principal investigator (or designee) to require delay or withdrawal from the infusion schedule. The investigator may consult with the HVTN 704/HPTN 085 PSRT.
- Pregnancy: for participants who become pregnant infusions will be stopped. If the participant is no longer pregnant (as demonstrated by a negative urine or serum pregnancy test) and wants to continue with infusions, the HVTN 704/HPTN 085 PSRT will be consulted to determine whether the participant may resume infusions or whether infusions should be permanently discontinued.

5.3.2 Participant departure from infusion schedule

Every effort should be made to follow the infusion schedule per the protocol. If a participant misses an infusion and the visit window period for the infusion has passed, then sites may consult the SSP.

5.3.3 Discontinuing infusions for a participant

Under certain circumstances, an individual participant's infusions will be permanently discontinued. Specific events that will result in stopping a participant's infusion schedule include:

- Co-enrollment in a study with an investigational research agent (rare exceptions allowing for the continuation of infusions may be granted with the unanimous consent of the HVTN 704/HPTN 085 PSRT);
- Clinically significant condition (ie, a condition that affects the immune system or for which continued infusions and/or blood draws may pose additional risk), including but not limited to the following:
 - Any grade 4 local or systemic reactogenicity symptom or AE that is subsequently considered to be related to study product;
 - An SAE that is subsequently considered to be related to study product;
 - Any grade 3 clinical AE (exception: fever or vomiting and subjective local and systemic symptoms) that is subsequently considered to be related to study product;
 - Any grade 3 or 4 lab abnormality confirmed by a repeated value that is subsequently considered to be related to study product;
 - Clinically significant hypersensitivity reaction including but not limited to type 1 hypersensitivity reaction and/or serum sickness associated with study product. Consultation with the HVTN 704/HPTN 085 PSRT is required prior to subsequent infusion following any hypersensitivity reaction associated with study product; or
- Investigator determination in consultation with Protocol Team leadership (eg, for repeated nonadherence to study staff instructions).

Infusions will be permanently discontinued for a participant diagnosed with HIV infection or with 2 reactive HIV tests, even if subsequent testing indicates that the participant is not HIV infected.

Participants for whom infusions are discontinued for reasons other than HIV infection should be counseled on the importance of continuing with the study and strongly encouraged to participate in Schedule 4 follow-up visits and protocol-specified procedures (see Appendix I and Appendix M), unless medically contraindicated.

5.3.4 Participant termination from the study

Under certain circumstances, an individual participant may be terminated from participation in this study. Specific events that will result in early termination include:

• Participant refuses further participation

- Participant relocates and remote follow-up or transfer to another CRS is not possible
- CRS determines that the participant is lost to follow-up
- Investigator decides, in consultation with Protocol Team leadership, to terminate participation (eg, if participant exhibits inappropriate behavior toward clinic staff)
- Any condition where termination from the study is required by applicable regulations.

6 Study product preparation and administration

CRS pharmacists should consult the Pharmacy Guidelines and Instructions for DAIDS Clinical Trials Networks for standard pharmacy operations. The protocol schema is shown in Table 1-1. See the IBs for further information about study products.

6.1 Study product regimen

The schedule of study product administrations is shown in Section 1 and additional information is given below.

Group 1

Treatment 1 (T1): VRC-HIVMAB060-00-AB 10 mg/kg in sufficient Sodium Chloride for Injection USP, 0.9% to prepare a final total volume of 150 mL to be administered IV at Weeks 0, 8, 16, 24, 32, 40, 48, 56, 64, and 72.

Group 2

Treatment 2 (T2): VRC-HIVMAB060-00-AB 30 mg/kg in sufficient Sodium Chloride for Injection USP, 0.9% to prepare a final total volume of 150 mL to be administered IV at Weeks 0, 8, 16, 24, 32, 40, 48, 56, 64, and 72.

Group 3

Control 3 (C3): Control for VRC01 (Sodium Chloride for Injection USP, 0.9%) to be prepared as a final total volume of 150 mL to be administered IV at Weeks 0, 8, 16, 24, 32, 40, 48, 56, 64, and 72.

6.2 Study product formulation

VRC-HIVMAB060-00-AB [VRC01, Labeled as VRC01 HIV MAb Drug Product VRC-HIVMAB060-00-AB]

VRC01 will be provided as a sterile clear, colorless to yellow isotonic solution, essentially free of visible particles; some opaque or translucent particles may be present. Each vial contains 100 mg / mL of VRC-HIVMAB060-00-AB in formulation buffer. The formulation buffer is composed of 25 mM sodium citrate, 50 mM sodium chloride, and 150 mM L-arginine hydrochloride at pH 5.8. Vials are intended for single use only and do NOT contain a preservative. The product should be stored frozen -35°C to -15°C with excursions permitted between -45°C and -10°C. The study products are described in further detail in the IB.

Prior to preparation, vials containing VRC01 must be removed from the freezer and thawed for a minimum of 1 hour at room temperature. Following this 1 hour thaw, the unopened vials of VRC01 may be stored for up to 24 hours at room temperature (not to exceed 27°C) and/or up to 4 weeks at 2°C to 8°C. Product may NOT be thawed or stored in direct sunlight. Once thawed, product may NOT be refrozen.

VRC01 is a highly concentrated protein solution and may develop white-to-translucent particles after thawing. These particles have been observed in approximately 1-3% of the vials and generally disappear over a few hours at room temperature. Particle formation has no effect on product quality. If the particles do not disappear at room temperature, the vials should be placed in the refrigerator, as particles may continue to dissipate at 2°C to 8°C (36°F to 46°F). Vials that continue to have visible particles after a maximum of 24 hours at controlled room temperature and/or after 4 weeks at 2°C to 8°C (36°F to 46°F) should not be used. Instead, those vials with particles still visible should be quarantined [at 2°C to 8°C (36°F to 46°F)] until they are returned to the NIAID Clinical Research Products Management Center (CRPMC) (or manufacturer upon request of the CRPMC) or destroyed if directed by the CRPMC.

Control for VRC01 [Sodium Chloride for Injection USP, 0.9%]

Sodium Chloride for Injection USP, 0.9% will be used as the Control for VRC01. It must be stored as directed by the manufacturer. For sites who do not have access to Sodium Chloride for Injection USP, 0.9%, the Sodium Chloride for Injection, 0.9% that they use must meet the following criteria: a sterile solution of Sodium Chloride in Water for Injection which contains no antimicrobial agents. It is nonpyrogenic and is intended for intravenous administration.

